7.2. Secondary Efficacy Analyses

7.2.1. Endpoint / Variables

- Plasma HIV-1 RNA and log₁₀ Plasma HIV-1 RNA on each assessment visit
- Change from baseline of plasma HIV-1 RNA and log₁₀ plasma HIV-1 RNA on each assessment visit
- Proportion of participants with plasma HIV-1 RNA <400 copies/mL and < 50 copies/mL
- Proportion of participants with plasma HIV-1 RNA change from baseline > 1.5 log₁₀ copies/mL decrease

7.2.2. Summary Measure

Descriptive summaries will include n, mean, standard deviation (SD), median, minimum, and maximum for continuous variables, whereas n and percent will be used as summary statistics for categorical variables.

7.2.3. Statistical Analyses / Methods

Details of the planned displays are provided in [Appendix 11](#): List of Data Displays and will be based on GSK data standards and statistical principles.

Unless otherwise specified, endpoints / variables defined in Section [7.2.1](#) will be summarised using descriptive statistics, graphically presented (where appropriate) and listed.

Plasma HIV-1 RNA will be listed by treatment, subject, and assessment visit and summarized by treatment and assessment visit along with change from baseline.

A plot of mean and median log₁₀ plasma HIV-1 RNA and change from baseline data will be generated by treatment and assessment visit.

7.3. Exploratory Efficacy Analyses

7.3.1. Immunology

7.3.1.1. Endpoint / Variables

- CD4+ and CD8+ T-cell count at each assessment visit along with change from baseline

7.3.1.2. Summary Measure

Descriptive summaries will include n, mean, standard deviation (SD), median, minimum, and maximum for continuous variables, whereas n and percent will be used as summary statistics for categorical variables.

In addition, mean rate of change for CD4+ T-cell count change from baseline to Visit 6 (Day 11 in Part 1 and Day 8 in Part 2) will be calculated based on the following linear mixed model.

7.3.1.3. Statistical Analyses / Methods

Details of the planned displays are provided in [Appendix 11](#): List of Data Displays and will be based on GSK data standards and statistical principles.

Unless otherwise specified, endpoints / variables defined in Section [7.3.1](#) will be summarised using descriptive statistics, graphically presented (where appropriate) and listed.

7.3.1.4. Statistical Methodology Specification

Endpoint / Variables

 Change from baseline in CD4+ T-cell count to Visit 6 (Day 11 in Part 1 and Day 8 in Part 2) (on log10 scale)
Model Specification

 Change from baseline to Visit 6 (Day 11 in Part or Day 8 in Part 2) in CD4+ T-cell count (on log10 scale) will be fitted in a mixed-effects linear model by treatment, with baseline CD4+ (on log10 scale) and VISIT fitted as fixed effects and subject fitted as a random effect.
Model Checking & Diagnostics

 Model assumptions will be applied, but appropriate adjustments may be made based on the data.
Model Results Presentation

 Statistical analysis for change from baseline will be presented in tabular format. The linear model will be used to estimate slope, intercept and a 90% CI of the slope. The model will be fitted for Part 1 and Part 2 data respectively. 
Example SAS Code:
 <pre>proc mixed data=dataset class dose visit subjid; model chgCD4 = baseCD4 visit dose; random subjid / type=un solution; run;</pre>
Sensitivity and Supportive Analyses
Both ITT and PP population will be used for the above analyses if PP population is differed from ITT population.

7.3.2. Clinical Virology

If virology data is available and up to analysis standards by DBF, viral genotypic and phenotypic data will be listed by treatment group, subject, and assessment day as in [Appendix 11](#): List of Data Displays and will be based on GSK data standards and statistical principles. If virology data is not available by DBF, a separate virology analysis report will be generated.

8. SAFETY ANALYSES

The safety analyses will be based on the Safety population, unless otherwise specified. Safety data will be presented in tabular format and summarized descriptively according to GSK's Integrated Data Standards Library standards and data will be in Clinical Data Interchange Standards Consortium (CDISC) format. No formal statistical analysis of the safety data will be conducted.

8.1. Adverse Events Analyses

Adverse events analyses including the analysis of adverse events (AEs), Serious (SAEs) and other significant AEs will be based on GSK Core Data Standards. The details of the planned displays are provided in [Appendix 11: List of Data Displays](#). The AE analysis will include part 1 and part 2 in one display (Part 1 placebo and Part 2 placebo displayed separately) for summary tables and listings.

The following summaries will be provided:

- Adverse events overview
- All adverse events by SOC and PT and all adverse events by maximum grade and SOC and PT
- Drug related adverse events by SOC and PT and drug related adverse events by maximum grade and SOC and PT
- Serious Adverse Events by SOC and PT (Number of Participants and Occurrences)
- Adverse events leading to withdrawal from study/permanent discontinuation of study treatment
- Common ($\geq 5\%$) adverse events by overall frequency
- Common ($\geq 5\%$) non-serious adverse events (Number of Subjects and Occurrences)

The following listings will be provided:

- All adverse events
- Subject numbers for individual AEs
- Serious adverse events
- Drug related adverse events
- Adverse events leading to withdrawal from study/permanent discontinuation of study treatment
- Fatal serious adverse events
- Non-fatal serious adverse events

8.2. Adverse Events of Special Interest Analyses

At the end of the study, all Cardiac System Organ Class / Preferred Terms, seizure, and syncope (regardless of Grade/Relationship), will be summarized by treatment. A listing will also be provided accordingly.

Gastrointestinal intolerability/toxicity AEs of special interest will be defined within three narrow sub-SMQs [Gastrointestinal nonspecific symptoms and therapeutic procedures

CONFIDENTIAL

208132

SMQ; Gastrointestinal nonspecific dysfunction SMQ; Gastrointestinal nonspecific inflammation (SMQ) plus a selection of relevant broad preferred terms from the Gastrointestinal non-specific symptoms and therapeutic procedures SMQ.

Psychiatric AEs of special interest will be defined within the following: Sub-SMQ 'Suicide/self-injury' (SMQ) from parent SMQ of 'Depression and Suicide/Self Injury'. Only narrow terms from the sub-SMQ selected.

Sub-SMQ 'Depression (excluding suicide and self-injury)' (SMQ) from parent SMQ of 'Depression and Suicide/Self Injury'. Only narrow terms from the sub-SMQ selected.

All preferred terms from HLGT 'Manic and Bipolar mood disorders and disturbances' under SOC 'Psychiatric disorders'.

narrow terms from SMQ 'Psychosis and psychotic disorders' selected.

All preferred terms from HLGT 'Anxiety disorders and symptoms', under SOC 'Psychiatric disorders'.

All preferred terms from HLGT 'Sleep Disorders and Disturbances' and HLGT 'Sleep disturbances (include subtypes)'

Nervous system disorders AEs of special interest will be defined within the following:

Four HLGTs under Nervous System Disorders SOC: "Headaches"; "Mental impairment disorders"; "Neurological disorders" and "Seizures"

8.3. Clinical Laboratory Analyses

Unless specified, clinical laboratory tables will be reported separately for Part 1 and Part 2. Corresponding listings will be paginated by part, sorted by participant, day, and time, noting treatment.

Haematology and clinical chemistry parameters collected are listed below.

CONFIDENTIAL

208132

Protocol-Required Safety Laboratory Assessments

Laboratory Assessments	Parameters			
Haematology	Platelet Count	RBC Indices:		White blood cells (WBC)
	Red blood cells (RBC) Count	Mean corpuscular volume (MCV)		count with Differential:
	Haemoglobin	Mean corpuscular haemoglobin (MCH)		Neutrophils
	Haematocrit	%Reticulocytes		Lymphocytes Monocytes Eosinophils Basophils
Clinical Chemistry ¹	BUN	Potassium	Aspartate Aminotransferase (AST)/ Serum Glutamic-Oxaloacetic Transaminase (SGOT)	Total and direct bilirubin
	Amylase and Lipase	Sodium, Bicarbonate, and Chloride	Alanine Aminotransferase (ALT)/ Serum Glutamic-Pyruvic Transaminase (SGPT)	Total Protein
	Glucose (nonfasting)	Calcium, Magnesium, and Phosphate	Alkaline phosphatase	Fasting Lipid Panel (Cholesterol, Triglycerides, High density lipoprotein [HDL], low density lipoprotein [LDL])
Routine Urinalysis	
 • Specific gravity • pH, glucose, protein, blood, ketones, bilirubin, urobilinogen, nitrite, leukocyte esterase by dipstick • Microscopic examination (if blood or protein is abnormal) 			
Other Screening Tests	
 • Follicle-stimulating hormone and estradiol (if needed to determine women of non-childbearing potential) • Urine human chorionic gonadotropin (hCG) pregnancy test (as needed)² • Serology (HIV antibody, hepatitis B surface antigen [HBsAg], and hepatitis C virus antibody [HCVAb], with reflex to HCV RNA if positive). • PCR (HIV-1 diagnostic PCR) 			

Laboratory Assessments	Parameters
	
 • Alcohol and drug screen (to include at minimum: amphetamines, barbiturates, cocaine, opiates, cannabinoids and benzodiazepines) • All study-required laboratory assessments will be performed by a central laboratory 
The results of each test may be entered into the CRF.

NOTES :

1. Details of liver chemistry stopping criteria and required actions and follow-up assessments after liver stopping or monitoring event are given in Section 8.1 and Appendix 7 All events of ALT $\geq 3 \times$ upper limit of normal (ULN) and bilirubin $\geq 2 \times$ ULN (>35% direct bilirubin) or ALT $\geq 3 \times$ ULN and international normalized ratio (INR) >1.5 , if INR measured, which may indicate severe liver injury (possible Hy's Law), must be reported as an SAE (excluding studies of hepatic impairment or cirrhosis).
2. Local urine testing will be standard for the protocol unless serum testing is required by local regulation or IRB/IEC.

Laboratory values, treatment emergent toxicities, and change from baseline for haematology, clinical chemistry, and liver function parameters will be summarized by visit and by treatment group. Laboratory values for haematology, clinical chemistry, liver function, and urinalysis will also be listed by subject. In addition, the number and percentage of participants with on-treatment laboratory abnormalities worsened from baseline by maximum grade will be reported for haematology, clinical chemistry. The participants with laboratory values of potential clinical importance will be summarised and listed (potential clinical importance criteria are specified in Section 13.8). The details of the planned displays are in Appendix 11: List of Data Displays.

8.4. Other Safety Analyses

The analyses of non-laboratory safety test results including ECGs, vital signs and Hepatobiliary will be based on GSK Core Data Standards, unless otherwise specified. Similar as clinical laboratory analysis, tables for other safety analyses will be reported separately for Part 1 and Part 2. Corresponding listings will be paginated by part, sorted by participant, day, and time, noting treatment. The details of the planned displays are presented in Appendix 11: List of Data Displays.

8.4.1. Electrocardiograms

ECG is collected triplicates at certain visits and for those visits average values will be reported in summary tables and triplicate readings will be listed in listings. A summary of the number and percentage of participants with ECG findings will be displayed by treatment. For abnormal ECG findings, the most recent one will be used if there's multiple records in the same visit. Additionally, summary statistics of change from baseline in ECG values will be presented. Maximum QTc values and maximum increase in QTc values post-baseline relate to baseline will be summarized by category. Mean (95% CI) change from baseline in QTcB-interval and QTcF interval will be plotted by time and treatment. All ECG Values for Participants with a Value of Potential Clinical Importance will be listed (potential clinical importance criteria are specified in Appendix

8: Values of Potential Clinical Importance). QTc interval data for subjects with QTc measurement > 500msec or increase from baseline > 60msec will also be listed.

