Preliminary GSK3640254 PK parameters derived based on nominal sampling times following single doses of 1 mg to 700 mg administered after a moderate calorie and fat breakfast show GSK3640254 is slowly absorbed with a median T_{max} observed between 3-4.5 hours after dosing with a moderate fat breakfast and slowly eliminated with a mean half-life ranging from 22-26 hours. In general, exposure (maximum observed concentration [C_{max}] and area under the curve [AUC]) increased in a close-to-dose-proportional manner from 1 mg to 400 mg with no further increase in exposure at 700 mg.

Repeat dose preliminary PK parameter following once-daily administration of 50 to 320 mg QD for 14 days were determined on Day 1 and Day 14 and show a median T_{max} ranging between 3.8 to 4.3 hours. The mean half-life ranged from approximately 22 to 29 hours. Overall, there was a trend of a slightly less than dose-proportional increase in C_{max} and AUC(0-24) from 50 to 320 mg. The exposure on Day 14 was, on average, 1.9 to 2.3 fold higher than that of Day 1 for C_{max} and 2.2 to 2.6 fold higher than Day 1 for

AUC(0-24). Detailed summary statistics are available in the Study Synopsis [GSK Document Number [2018N375461_00](#)].

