3.3. Benefit/Risk Assessment

Based upon pre-clinical and clinical studies with the prior MI GSK3532795 and the current molecule GSK3640254, the major risks are GI intolerability (e.g. abdominal pain and diarrhoea) and toxicity, prolongation of QTc, neuropsychiatric safety, and treatment

emergent resistance to GSK3640254. If present, preclinical GI toxicity findings (e.g. single cell parietal cell necrosis) in subjects would be minimal and not be persistent upon discontinuation of GSK3640254 after 7 days of dosing. The risk of GI intolerability and neuropsychiatric safety is described in Section 3.3.1. The risk for QTc prolongation is described below in Section 3.3.1 where one pre-clinical study did show one dog with an increased QTc interval when given a single dose of GSK3640254. As described in Section 3.2.2, a cardiodynamic analysis of healthy subjects in Study 207187 was conducted. A final model from the MAD data showed a QT effect ($\Delta\Delta\text{QTcF}$) of GSK3640254 could be predicted to be 5.38 ms (90% CI: 1.66 to 9.10) and 6.70 ms (90% CI: 2.79 to 10.61) for the 200 mg (1779 ng/mL) and 320 mg (2154 ng/mL) doses, respectively, on Day 14. Based on this concentration-QTc analysis, a QTcF effect above 10 ms could be excluded up to GSK3640254 plasma concentrations of approximately 2000 ng/mL (corresponding to doses approximately ≤ 200 mg QD; note, 200 mg QD was the maximum dose used in Part 1 of this study 208132). Importantly, there were no abnormal clinically significant arrhythmias or QTc prolongations (values >500 ms or increases >60 ms from Baseline) in Study 207187. This study contains specific cardiac exclusion criteria, has ECG monitoring (at Tmax once GSK3640254 attains steady state concentration), and has QTcF based stopping criteria.

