	Day 1	Day 2	Day 3, 4 Choose one day for the Clinic Visit 3. The other day will be a virtual event.		Day 5, 6, 7 Choose one day for the Clinic Visit 4. The other days will be virtual events.			Day 8, 9, 10 Choose one day for the Clinic Visit 5. The other days will be virtual events.			Day 11	Day 12	Day 13, 14, 15, 16 or 17	Day 18, 19, 20, 21, 22, 23 or 24
	Clinic Visit 1	Clinic Visit 2	Clinic Visit 3	Virtual	Clinic Visit 4	Virtual	Virtual	Clinic Visit 5	Virtual	Virtual	Clinic Visit 6	Clinic Visit 7	Clinic Visit 8	Clinic Visit 9
Clinical Procedures														
12-lead ECG (triplicate reading, pre-dose; single readings at PK draws 2hr, 4hr, and 6hr)	X													
12-lead ECG (single reading, pre-dose at Visits 2 and 3)		X	X											X
12-lead ECG (single reading pre-dose and at PK draws 2hr, 4hr, and 6hr)								X						
Pharmacogenetics (PGX) Collection (if consented)	X													

CONFIDENTIAL

208132

Procedure ¹	Treatment Period Day 1 – Day 10									Post-Dosing Follow Up Period Day 11 – 17			Final Follow-up Day 18-24	
	Day 1	Day 2	Day 3, 4 Choose one day for the Clinic Visit 3. The other day will be a virtual event.		Day 5, 6, 7 Choose one day for the Clinic Visit 4. The other days will be virtual events.			Day 8, 9, 10 Choose one day for the Clinic Visit 5. The other days will be virtual events.			Day 11	Day 12	Day 13, 14, 15, 16 or 17	Day 18, 19, 20, 21, 22, 23 or 24
	Clinic Visit 1	Clinic Visit 2	Clinic Visit 3	Virtual	Clinic Visit 4	Virtual	Virtual	Clinic Visit 5	Virtual	Virtual	Clinic Visit 6	Clinic Visit 7	Clinic Visit 8	Clinic Visit 9
Hematology/Chemistry/Urine	X	X	X		X			X			X			X
Fasting Lipid Panel (approximately 8 hrs)	X										X			X
Lymphocyte T-cell subsets (CD4, CD8)	X										X			
Plasma for HIV-1 genotype/phenotype ⁵	X	X	X		X			X			X	X	X	X
Plasma for storage ⁶	X	X	X		X			X			X	X	X	X
HIV-1 RNA	X	X	X		X			X			X	X	X	X

CONFIDENTIAL

208132

Procedure ¹	Treatment Period Day 1 – Day 10									Post-Dosing Follow Up Period Day 11 – 17			Final Follow-up Day 18-24	
	Day 1	Day 2	Day 3, 4 Choose one day for the Clinic Visit 3. The other day will be a virtual event.		Day 5, 6, 7 Choose one day for the Clinic Visit 4. The other days will be virtual events.			Day 8, 9, 10 Choose one day for the Clinic Visit 5. The other days will be virtual events.			Day 11	Day 12	Day 13, 14, 15, 16 or 17	Day 18, 19, 20, 21, 22, 23 or 24

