Procedure ¹	Treatment Period Day 1 – Day 7						Post-Dosing Follow Up Period	Final Follow- up	
	Day 1	Day 2	Day 3, 4 Choose one day for the Clinic Visit 3. The other day will be a virtual event.		Day 5, 6 Choose one day for the Clinic Visit 4. The other day will be a virtual event.		Day 7	Day 8	Day 10, 11 or 12
	Clinic Visit 1	Clinic Visit 2	Clinic Visit 3	Virtual	Clinic Visit 4	Virtual	Clinic Visit 5	Clinic Visit 6	Clinic Visit 7
Clinical Procedures									
12-lead ECG (triplicate reading, done pre-dose; single readings at PK draws 2hr, 4hr, and 6hr)	X								
12-lead ECG (single reading, done pre-dose at Visits 2 and 3)		X	X						X
12-lead ECG (single reading done pre-dose and at PK draws 2hr, 4hr, and 6hr)							X		

CONFIDENTIAL

208132

Procedure ¹	Treatment Period Day 1 – Day 7						Post-Dosing Follow Up Period	Final Follow- up	
	Day 1	Day 2	Day 3, 4 Choose one day for the Clinic Visit 3. The other day will be a virtual event.		Day 5, 6 Choose one day for the Clinic Visit 4. The other day will be a virtual event.		Day 7	Day 8	Day 10, 11 or 12
	Clinic Visit 1	Clinic Visit 2	Clinic Visit 3	Virtual	Clinic Visit 4	Virtual	Clinic Visit 5	Clinic Visit 6	Clinic Visit 7
Pharmacogenetics (PGX) Collection (if consented)	X								
Hematology/Chem istry/Urine	X	X	X		X		X	X	X
Fasting Lipid Panel (approximately 8 hrs)	X							X	X
Lymphocyte T-cell subsets (CD4, CD8)	X							X	
Plasma for HIV-1 genotype/phenoty pe ⁵	X	X	X		X		X	X	
Plasma for storage ⁶	X	X	X		X		X	X	X

CONFIDENTIAL

208132

Procedure ¹	Treatment Period Day 1 – Day 7						Post-Dosing Follow Up Period	Final Follow- up	
	Day 1	Day 2	Day 3, 4 Choose one day for the Clinic Visit 3. The other day will be a virtual event.		Day 5, 6 Choose one day for the Clinic Visit 4. The other day will be a virtual event.		Day 7	Day 8	Day 10, 11 or 12
	Clinic Visit 1	Clinic Visit 2	Clinic Visit 3	Virtual	Clinic Visit 4	Virtual	Clinic Visit 5	Clinic Visit 6	Clinic Visit 7
HIV-1 RNA	X	X	X		X		X	X	X
Single, Pharmacokinetic (PK) sample done pre-dose			X		X				
Intensive PK sampling (to include the 24hr samples drawn the next day)	X						X		
Observed dosing with GSK3640254 /placebo ³	X	X	X	X	X	X	X		

CONFIDENTIAL

208132

Procedure ¹	Treatment Period Day 1 – Day 7						Post-Dosing Follow Up Period	Final Follow- up	

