13.3. Appendix 3: Assessment Windows**13.3.1. Definitions of Assessment Windows for Analyses**

Analyses will be presented by scheduled visits as collected in the CRF. The following table presents protocol defined assessment windows.

Part 1

Analysis Set / Domain	Parameter (if applicable)	Target	Analysis Window		Analysis Timepoint
			Beginning Timepoint	Ending Timepoint	
Safety and Efficacy	All	14 - 28 days prior to first dose	28 days prior to first dose	Day -1	Screen
Efficacy	HIV-1 RNA, HIV-1 genotype / phenotype	Day 1	Day 1	Day 1	Visit 1
		Day 2	Day 2	Day 2	Visit 2
		Day 3 or 4	Day 3	Day 4	Visit 3
		Day 5, 6, or 7	Day 5	Day 7	Visit 4
		Day 8, 9, or 10	Day 8	Day 10	Visit 5
		Day 11	Day 11	Day 11	Visit 6
		Day 12	Day 12	Day 12	Visit 7
		Day 13, 14, 15, 16, or 17	Day 13	Day 17	Visit 8
		Days 18 to final follow up visit day	Day 18	final follow up visit day	Follow-up
	CD4 and CD8	Day 1	Day 1	Day 1	Visit 1
Day 11		Day 11	Day 11	Visit 6	
Safety	Laboratory: Chemistry/ Haematology/ Urinalysis	Day 1	Day 1	Day 1	Visit 1
		Day 2	Day 2	Day 2	Visit 2
		Day 3 or 4	Day 3	Day 4	Visit 3
		Day 5, 6, or 7	Day 5	Day 7	Visit 4
		Day 8, 9, or 10	Day 8	Day 10	Visit 5
		Day 11	Day 11	Day 11	Visit 6
		Days 18 to final follow up visit day	Day 18	final follow up visit day	Follow-up
	Fasting Lipid Panel	Day 1	Day 1	Day 1	Visit 1
		Day 11	Day 11	Day 11	Visit 6
		Days 18 to final follow up visit day	Day 18	final follow up visit day	Follow-up
	ECG	Day 1 ¹	Day 1	Day 1	Visit 1
		Day 2 ²	Day 2	Day 2	Visit 2
		Day 3 or 4 ²	Day 3	Day 4	Visit 3
Day 8, 9, or 10 ³		Day 8	Day 10	Visit 5	
Days 18 to final follow up visit day ²		Day 18	final follow up visit day	Follow-up	

CONFIDENTIAL

208132

Analysis Set / Domain	Parameter (if applicable)	Target	Analysis Window		Analysis Timepoint
			Beginning Timepoint	Ending Timepoint	
	Vital Signs	Day 1	Day 1	Day 1	Visit 1
		Day 2	Day 2	Day 2	Visit 2
		Day 3 or 4	Day 3	Day 4	Visit 3
		Day 8, 9, or 10	Day 8	Day 10	Visit 5
		Days 18 to final follow up visit day	Day 18	final follow up visit day	Follow-up

NOTES:

¹ 12-lead ECG (triplicate reading, pre-dose; single readings at PK draws 2hr, 4hr, and 6hr)

² 12-lead ECG (single reading, pre-dose)

³ 12-lead ECG (single reading pre-dose and at PK draws 2hr, 4hr, and 6hr)

Part 2

Analysis Set / Domain	Parameter (if applicable)	Target	Analysis Window		Analysis Timepoint
			Beginning Timepoint	Ending Timepoint	
Safety and Efficacy	All	14 - 28 days prior to first dose	28 days prior to first dose	Day -1	Screen

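### The most-recent-record rule for abnormal ECG findings can leave a 2 h or 4 h abnormality, or the worse of two, out of Tables 3.43 and 3.44

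*SAP*

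**What the plan says.** SAP 8.4.1 plans a participant-level count: "A summary of the number and percentage of participants with ECG findings will be displayed by treatment". It then adds: "For abnormal ECG findings, the most recent one will be used if" several records fall in the same visit. The list of displays in SAP Appendix 11 implements this as Tables 3.43 (Part 1) and 3.44 (Part 2), both marked for the headline report.

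Several records per visit are the schedule, not an accident. In SAP Appendix 2, Visit 1 has "12-lead ECG (triplicate reading, pre-dose; single readings at PK draws 2hr, 4hr, and 6hr"). Visit 5 in Part 2 has "12-lead ECG (single reading done pre-dose and at PK draws 2hr, 4hr, and 6hr"), and Part 1 has the same set at its Visit 5. The ECG rows of SAP Appendix 3 assign each of these days to one analysis time point, Visit 1 or Visit 5, with the tracings described only in a footnote: "12-lead ECG (single reading pre-dose and at PK draws 2hr, 4hr, and 6hr").

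On timing, Protocol 3.2.2 reports a median repeat-dose Tmax in healthy participants "ranging between 3.8 to 4.3 hours". Protocol 3.3 lists among the safeguards that the study "has ECG monitoring (at Tmax once GSK3640254 attains steady state concentration").

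**The concern.** A summary of safety findings normally keeps the worst observation in a period. A last-record rule keeps whichever came latest, and at both intensive visits the last scheduled tracing falls after the one nearest the expected peak concentration. A transient rhythm or conduction finding at 2 or 4 h could therefore be recorded by the site and still be missing from the count of participants with abnormal findings.

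The rule is also out of step with the rest of the SAP. Vital signs use the worst case (8.4.2), laboratory abnormalities use maximum grade and worst-case shifts (8.3; Tables 3.15, 3.16, 3.25 and 3.26), and QTc uses the post-baseline maximum (8.4.1). No reason is given for treating ECG findings differently.

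At stake is the accuracy of two descriptive tables. They matter somewhat more than their descriptive status suggests. They are the only ECG summary tables in the headline report, and no maximum or worst-case table is planned for PR, QRS or qualitative findings. Protocol 3.3.1 records that the compound inhibited cardiac sodium and L-type calcium currents as well as hERG, so findings other than QTc are of interest.

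**Working it through.** The plan gives no figure to reproduce. The check traces the rule through the schedule and the displays, then illustrates the possible size.

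**1. Where the rule applies.** From SAP Appendix 2:
- Visit 1: triplicate pre-dose, then single tracings at 2, 4 and 6 h.
- Visit 5: single tracings pre-dose and at 2, 4 and 6 h, so four records.
- Visits 2 and 3 and the final follow-up: one scheduled reading, so nothing to choose between.

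The rule is therefore engaged for every participant at two visits.

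**2. Which record is kept.** The last scheduled record at Visits 1 and 5 is the 6 h tracing. With median Tmax between 3.8 and 4.3 h, the 4 h tracing is nearest the peak; 2 h precedes it.

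**3. Two readings of the sentence.**
- *Latest record of any kind.* Abnormal at 4 h and normal at 6 h gives a normal entry. One of the four Visit 5 tracings decides the entry.
- *Latest abnormal record.* Abnormal at 4 h and normal at 6 h stays abnormal. A more serious abnormality at 4 h followed by a lesser one at 6 h is entered as the lesser.

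Neither reading gives the worst finding.

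**4. Which displays are affected.**
- Governed by the rule: Tables 3.43 and 3.44.
- Not governed: maximum QTc and maximum QTc increase by category (Tables 3.47 to 3.50); display 3.51, which shows all time points for participants with QTc above 500 msec or an increase above 60 msec; QTc change by time (Figures 3.1 and 3.2); and Listings 28 and 29.

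**5. Illustration of size, first reading only.** Assume each post-dose tracing is abnormal with probability p, independently. Neither p nor independence comes from the documents.
- Counted on any of 2, 4 and 6 h: 1 − (1 − p)³. Counted on 6 h alone: p.
- p = 5%: 1 − 0.95³ = 14.3%, against 5%. Share not counted: 1 − 5/14.3 = 65%.
- p = 10%: 1 − 0.90³ = 27.1%, against 10%. Share not counted: 1 − 10/27.1 = 63%.
- A finding that persists to 6 h: no loss.

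Active cohorts have 6 participants, so each one not counted is 1/6 = 16.7 percentage points.

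**The case against.** The best case for the plan has several parts.

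- **Wording.** The sentence opens with abnormal findings, so the latest of several abnormal records is a natural reading. A normal 6 h tracing then displaces nothing.
- **Purpose.** The paragraph begins with triplicates, whose numeric values are averaged. Categorical findings cannot be averaged, so the rule may be meant only as a tie-break for replicates.
- **Summaries by time.** SAP 13.5.2 uses planned time relative to dosing in summaries, and Protocol 10.3.2 presents summaries by visit and time. Tables 3.43 and 3.44 follow a standard shell, EG1, that is not in the documents. It may already have rows by time or an any-time post-baseline row.
- **Coverage elsewhere.** The named cardiac risk is QT prolongation, and the QTc displays use every post-baseline time. Listings 28 and 29 are headline deliverables. ECG abnormalities judged clinically significant meet the adverse event definition (Protocol Appendix 4), and cardiac events are summarised under SAP 8.2.
- **6 h is close to peak.** Protocol Table 2 predicts 1629 ng/mL at Cmax and 809 ng/mL at 24 h for 200 mg. With log-linear decline from about 4 h, the rate is ln(1629/809)/20 = 0.035 per hour, so the 6 h level is about 1 − exp(−0.07) = 7% below peak. An effect driven by concentration would often still be visible.

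Much of this stands. It limits the point to two tables and makes the size uncertain. It does not remove the point. The sentence refers to records in the same visit, not to replicates at one time, and two programmers could produce different counts from it. The latest-abnormal reading still lets a lesser finding replace a worse one.

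A reader might infer that the rule defeats the protocol's ECG monitoring near Tmax. The documents do not support that: the tracings are still taken, and the QTcF stopping criteria in Protocol 8.1.2 apply to on-treatment ECGs whatever a summary table shows.

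**Conclusion.** The concern holds in limited form. As written, the rule is ambiguous, and neither reading gives the worst finding at the visits with serial tracings. Read literally, it can remove a 2 h or 4 h abnormality from Tables 3.43 and 3.44; on the other reading it can understate severity.

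A reader might go further and conclude that peak-time abnormalities disappear from the ECG tables in general. They do not: QTc peaks remain in Tables 3.47 to 3.50, and abnormal findings remain in Listing 29. Nor can the loss be stated as a fact. The 14.3% against 5% and 27.1% against 10% rest on an assumed rate, on independent tracings within a participant and on the literal reading. Positive correlation between tracings would shrink the gap, to nothing for findings that persist to 6 h. The layout of the EG1 shell is also unknown. Safety is descriptive and no decision rule uses these tables, so this is a worthwhile correction rather than a threat to the trial's conclusions.

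**What to change.** Replace the sentence in SAP 8.4.1 with:

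*Where a visit has more than one ECG record, the worst post-baseline finding (most severe category in the table shell) is used for the visit and for any any-time post-baseline row; Day 1 pre-dose records are used as baseline only.*

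Apply it to Tables 3.43 and 3.44. Tying severity to the shell's own categories avoids assuming what EG1 contains. The Visit 5 pre-dose tracing is post-baseline and would count.

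The cost is one sentence and a small programming change. Abnormality counts may be slightly higher than under the present rule.
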